13.8.1 Handling of Missing Data for PK Analyses

While no data exclusions or imputations are planned, they may be made in the case of implausible or outlier data. Such cases will be adjudicated by a trained pharmacokineticist and reported with justification. In cases where imputations or exclusions may affect the conclusions or interpretation of the results significantly, an assessment of such impact may be conducted, at the discretion of the pharmacokineticist, by comparing the results with and without such actions. All imputations and exclusions need to be approved by the sponsor upon discussing the justification, and imputations and exclusions will be documented in the report along with the justification.

13.8.2 Plasma Concentrations

Serum levels with below quantification level (BQL) results at the beginning of the profile (i.e. before the first measurable serum levels) are given a value of zero. BQL at end of profile (eg 48 hr) should be replaced with 1/2 LLOQ= 1 ng/mL). BLQ values embedded between two measurable values will be imputed as zero. For serum levels Above Level of Quantification (ALQ) the upper limit of quantification will be used.

Descriptive statistics (n, mean, SD, coefficient of variation % (%CV), median, minimum, maximum, geometric mean, and geometric CV) of PK concentration will be presented by period, visit, dose and timepoint for Period 1 and by period, visit, and timepoint for Period 2 and Period 3. Data listings of individual subject concentrations by time point, visit and period will be provided (unscheduled results will not be included in the listing).

In addition, the mean plasma concentrations and individual subject plasma concentrations will be presented in both the linear and semi-log scales by period, visit and timepoint.

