11.0 Analysis Sets

11.1 Safety Analysis Set

The safety analysis set is defined as all subjects who received at least one dose of study drug in the considered period.

The main objective of the study is to characterize the safety of subjects with ADH1 treated with CLTX-305 (encaleret). All analyses of the safety and efficacy (PD) data will be performed using the safety analysis set.

- For Period 1, unless otherwise specified, all descriptive statistics will be presented by dose level and by day (and timepoint where applicable).
- For Period 2, unless otherwise specified, all descriptive statistics will be presented by day (and timepoint where applicable).
- For Period 3 and LTE, all descriptive statistics will be presented by period (and timepoint where applicable).

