13.0 Statistical Methods

All data collected during this study will be displayed in data listings. Data listings will be sorted by period, cohort, and subject identifier. In addition, listings will include all relevant derived variables. The summary tables will be presented for by period, and by visit and timepoint when relevant.

Demographic and baseline summaries will be presented for each period; periods may be combined if the same subjects are included (and the data summarized is the same). Unless otherwise noted, categorical variables will be summarized using counts and percentages. Percentages will be rounded to one decimal place, except 100% will be displayed without any decimal places and percentages will not be displayed for zero counts.

Continuous variables will be summarized using the number of observations (n), mean, standard deviation (SD), median, minimum and maximum. The first and third quartile estimates (Q1 and Q3) will additionally be reported in descriptive analyses of continuous variables.

Summary statistics will be tabulated for each of the PK parameters by dose level and by study day separately for Period 1 and Period 2. Geometric means and coefficients of variation will be presented for C_{max} , C_{trough} , AUC_{0-t} , AUC_{0-24} , AUC_{0-inf} , AUC_{0-tau} , and $T_{1/2}$. Median, minimum and maximum will be presented for T_{max} . Actual times will be used for PK parameter reporting unless they are not available. In such cases nominal times will be used.

The mean, median, Q1 and Q3 values will be displayed with 1 decimal place, the minimum and maximum will be displayed with 0 or 1 decimal place depending on the data and the SD will be displayed with two additional decimal places. For fractional calcium excretion, the mean, median, minimum, maximum, Q1, Q3 and SD values will be displayed with 3 decimal places.

No formal statistical tests will be performed on efficacy variables; however, post-hoc inferential statistics will be carried out for specific parameters. Statistical hypothesis testing will be 2-tailed and carried out at the 5% level of significance.

All analyses will use SAS version 9.4 or higher.

This is a single site study. No subgroup analyses will be performed. No adjustments for multiplicity will be made.

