13.8.3 Pharmacokinetics (PK) Data Analysis Methods

PK parameter estimates for CLTX-305 (encaleret) in plasma will be calculated by ICON using standard noncompartmental methods of analysis found in WinNonlin Phoenix version 8.1 or higher (Certara, Princeton, NJ, USA).

For calculation of AUC, BQL values on the leading edge of the profile (i.e., before t_{max}) are set equal to zero in the dataset loaded into WinNonlin (WNL) for PK analysis. BQL values after t_{max} are set to missing. BLQ values embedded between two measurable values will be treated as missing. Actual times will be used in the calculation of PK parameters. If actual times are missing, then nominal times will be used.

Descriptive statistics (n, mean, SD, %CV, median, minimum, maximum, geometric mean, and geometric CV) of PK parameters will be presented for each study dose, visit and period.

PK of CLTX-305 (encaleret) will be assessed by measuring the PK parameters included in Table 7.

Parameter	Description	PK Analysis Notes	SAS Programming Notes
C _{max}	Maximum plasma concentration. Observed peak analyte concentration obtained directly from the experimental data without interpolation, expressed in concentration units	single and multiple doses	Cmax from WNL
t _{max}	Time to reach Cmax in plasma. The time to reach maximum concentration is obtained directly from the experimental data without interpolation and expressed in time units.	single doses and multiple doses	Tmax from WNL

Table 7: PK Parameters

Parameter	Description	PK Analysis Notes	SAS Programming Notes
t _{1/2}	Terminal elimination phase half-life expressed in time units. $t_{1/2}$, will be calculated as ln2/Lambda z, where Lz is as defined below.	Single dose If there is no valid terminal phase and terminal elimination rate constant (Lambda z), t _{1/2} cannot be calculated	HL_Lambda_z from WNL Flag to List only if: AUC_%_obs >20% OR Rsq_< 0.8
Lambda z	First-order rate constant associated with the terminal (log-linear) portion of the curve. Estimated by linear regression of time vs. log concentration.	Single dose	Lambda_z from WNL Flag to list only
AUC _{0-t}	Area under the concentration-time curve from time 0 (dosing) to the time of the last quantifiable concentration AUC(0-T) is expressed in concentration*time units.	Single dose Calculated by the linear up/log down method in WNL.	AUClast from WNL

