16.1.2 PD sampling

Table 12: Non-intensive BID Sampling Days

Period 1: Day 4 (BID Dosing) and Period 3: PK/PD sampling days

	Timepoint ± 20 min. (relative to AM dose)						
Blood Assays							
PK ¹ samples	-15 min, +30 min, 2, 4, 8, 11, 13 hrs						
Intact PTH	-15 min, +30 min*, 2, 4, 8, 11, 13, 17 hrs						
Serum bone markers: CTX, P1NP	-15 min, 13 hrs						
1, 25-(OH) ₂ Vitamin D, cAMP	-15 min, 4, 8, 13, 17, 24 hrs ²						
Ca, PO4, Mg, Cr, albumin	-15 min, +30 min*, 2, 4, 8, 11, 13, 17, 24 hrs ²						
К, СК	-15 min, 13 hrs						
Urine Assays:							
Timed Interval Urine Collections: Ca, Mg, PO ₄ , Cr, cAMP, pH	-15 min 0-4 h, 4-8 h, 8-13 h, 13-17 h, 17-24 h						
24-Hour urine: Ca, Mg, PO ₄ , Cr, Na, K, Citrate, pH	0, 24 hrs (Start collection after first morning void and end 24 hours later)						

Abbreviations: Ca = Calcium; CK = Creatine Kinase; Cr = Creatinine; CTX = C-telopeptide; K = Potassium; Mg = Magnesium; Na = Sodium; P1NP = Procollagen type 1 N-propeptide; PK = Pharmacokinetics; PO₄ = Phosphate; PTH = Parathyroid hormone.

¹ PK in Period 3 only collected at 24 weeks;

² 24 hour timepoint only collected in Period 3

* +30 min timepoint only collected in Period 3 at 24 weeks

Table 13: Non-intensive BID Sampling Days - (if CLTX-305 (encaleret) dose is ≤ 180 mg BID)

Period 2: Days 1, 2, 3 & 4

	Timepoint ± 20 min. (relative to AM dose)
Blood Assays	
PK samples	-15 min, 2, 4 hrs
Intact PTH	-15 min, +30 min, 2, 4, 8, 11, 13, 17 hrs
1, 25-(OH) ₂ Vitamin D	-15 min, 4, 8 hrs
Ca, PO4, Mg, Cr, albumin	-15 min, +30 min, 2, 4, 8, 11, 13, 17 hrs
K, CK	-15 min, 13 hrs
Urine Assays:	
Timed Interval Urine Collections: Ca, Mg, PO ₄ , Cr, pH	-15 min ¹ , 0-4 h, 4-8 h, 8-13 h, 13-17 h, 17-24 h
24-Hour urine: Ca, Mg, PO ₄ , Cr, Na, K, Citrate, pH	0, 24 hrs (Start collection after first morning void and end 24 hours later)

Abbreviations: Ca = Calcium; CK = Creatine Kinase; Cr = Creatinine; K = Potassium; Mg = Magnesium; Na = Sodium; PK = Pharmacokinetics; PO₄ = Phosphate; PTH = Parathyroid hormone.

¹ -15 min urine is done on Period 2 (Day 1) only

Table 14: Non-intensive BID Sampling Days - (if CLTX-305 (encaleret) dose is > 180 mg BID)

Period 2: Days 2, 3 & 4

	Timepoint ± 20 min. (relative to AM dose)
Blood Assays	
PK samples	-15 min, +30 min, 2, 4, 8, 11, 13 hrs
Intact PTH	-15 min, +30 min, 2, 4, 8, 11, 13, 17 hrs
1, 25-(OH) ₂ Vitamin D	-15 min, 4, 8,
Ca, PO4, Mg, Cr, albumin	-15 min, +30 min, 2, 4, 8, 11, 13, 17 hrs
К, СК	-15 min, 13 hrs
Urine Assays:	

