Abbreviation: TRT = Time Relative To; Ca = Calcium; CK = Creatine Kinase; Cr = Creatinine; CTX = C-telopeptide; K = Potassium; Mg = Magnesium; Na = Sodium; P1NP = Procollagen type 1 N-propeptide; PK = Pharmacokinetics; PO₄ = Phosphate; PTH = Parathyroid hormone.

Table 17: Intensive Sampling Days for BID dosing - (if CLTX-305 (encaleret) dose is > 180 mg BID)

Period 2: Day 5

	Timepoints ± 10 min (relative to AM & PM doses)			
Blood Assays				
PK samples	TRT AM Dose: -15 min, +30 min, 1.5, 2, 4, 6, 8 hrs			
	TRT PM Dose: +30 n	nin, 1.5, 2, 4, 6, 15 hrs		
Intact PTH	TRT AM Dose: -15 min, +30 min, 1.5, 2, 4, 6, 8 hrs			
	TRT PM Dose: +30 m	nin, 1.5, 2, 4, 6, 8, 15 hrs		
Ca, PO4, Mg, Cr, albumin	TRT AM Dose: -15 min, +30 m	nin, 1.5, 2, 4, 6, 8 hrs		
	TRT PM Dose: +30 n	nin, 1.5, 2, 4, 6, 8, 15 hrs		
К, СК	TRT AM Dose: -15 min, 8 hrs			
Urine Assays				
Timed Interval Urine Collections: Ca, Mg, PO ₄ , Cr, pH	0-4 h, 4-8h, 8-13h, 13-17h, 17-24 h			
24-Hour urine: Ca, Mg, PO4, Cr, Citrate, Na, K, pH	0-24 h (Start collection after first morning void and end 24 hours later)			

Abbreviation: TRT = Time Relative To; Ca = Calcium; CK = Creatine Kinase; Cr = Creatinine; K = Potassium; Mg = Magnesium; Na = Sodium; PK = Pharmacokinetics; PO_4 = Phosphate; PTH = Parathyroid hormone.

Table 18: Intensive Sampling Days for BID dosing- (if CLTX-305 (encaleret) dose is ≤ 180 mg BID)

Period 2: Day 5

	Timepoints ± 10 min (relative to AM & PM doses)			
Blood Assays				
PK samples	TRT AM Dose: -15 min, 1.5, 4 h			
	TRT PM Dose: +30 min, 1.5, 4, 15 h			
Intact PTH	TRT AM Dose: -15 min, 1.5, 4, 8 hrs			
	TRT PM Dose: +30 min, 1.5, 4, 8, 15 hrs.			
Serum bone markers: CTX, P1NP	TRT AM Dose: -15 min 8 hrs.			
1, 25-(OH) ₂ Vitamin D, cAMP	TRT AM Dose: -15 min4, 8 hrs.			
	TRT PM Dose: 4, 8, 15 hrs.			
Ca, PO4, Mg, Cr, albumin	TRT AM Dose: -15 min, 1.5, 4, 8 hrs.			
	TRT PM Dose: +30 min, 1.5, 4, 8, 15 hrs.			
К, СК	TRT AM Dose: -15 min, 8 hrs.			
Urine Assays				
Timed Interval Urine Collections: Ca, Mg, PO4, Cr, cAMP, pH	0-4 h, 4-8h, 8-13h, 13-17h, 17-24 h			
24-Hour urine: Ca, Mg, PO ₄ , Cr, Citrate, Na, K, pH	0-24 h (Start collection after first morning void and end 24 hours later)			

Abbreviation: TRT = Time Relative To; Ca = Calcium; CK = Creatine Kinase; Cr = Creatinine; CTX = C-telopeptide; K = Potassium; Mg = Magnesium; Na = Sodium; P1NP = Procollagen type 1 N-propeptide; PK = Pharmacokinetics; PO₄ = Phosphate; PTH = Parathyroid hormone.

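### SAP 13.8.2 pools individually titrated doses in the Period 2 and Period 3 concentration summaries and mean plots, although PK parameters are shown by dose and Period 2 sampling times depend on dose

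*SAP*

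**What the plan says.** **Concentrations.** SAP 13.8.2 gives descriptive statistics (n, mean, SD, CV, median, range, geometric mean and geometric CV) "by period, visit, dose and timepoint for Period 1 and by period, visit, and timepoint for Period 2 and Period 3". Mean and individual profiles "will be presented in both the linear and semi-log scales by period, visit and timepoint", with no dose factor.

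**Parameters.** SAP 13.0 tabulates summary statistics "for each of the PK parameters by dose level and by study day separately for Period 1 and Period 2". SAP 13.8.3 says that descriptive statistics "of PK parameters will be presented for each study dose, visit and period". Protocol 9.7 asks for PK parameters by treatment and sets no grouping for concentrations.

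**General convention.** SAP 11.1 states: "For Period 2, unless otherwise specified, all descriptive statistics will be presented by day (and timepoint where applicable"). Period 1 is by dose level and day; Period 3 is by period.

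**Sampling.** On Period 2 Day 5 the morning PK samples above 180 mg BID are "TRT AM Dose: -15 min, +30 min, 1.5, 2, 4, 6, 8 hrs" (SAP Table 17). At 180 mg BID or below they are "TRT AM Dose: -15 min, 1.5, 4 h" (Table 18). Days 2-4 differ in the same way (Table 14 against Table 13). Week 24 follows one schedule, Table 12, at every dose.

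**AUC0-tau.** SAP 9.0 plans Period 2 Day 5 parameters whatever the dose. SAP Table 7 sets tau at 9 h for the morning dose and 15 h for the evening dose, by the linear up/log down method.

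**The concern.** A mean or CV taken across people on different doses does not describe exposure at any dose, and part of the spread it reports is simply dose mix. A reader comparing the concentration tables with the parameter tables finds one pooled and the other by dose.

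In Period 2 there is a possible second effect. Some timepoints exist only for participants above 180 mg BID. A mean curve drawn through all timepoints could then move up or down because the contributing people change and not because the drug level does.

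A smaller, related matter is the morning AUC0-tau on Day 5. For anyone sampled under Table 18 it needs 5 h of curve that nobody observed, and the visible text does not require the value to be flagged.

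**Working it through.** **1. Tau, reproduced.** SAP 10.3 equates the evening 4, 8 and 15 h samples with 13, 17 and 24 h after the morning dose. 13 - 4 = 17 - 8 = 24 - 15 = 9 h, and 24 - 9 = 15 h. Both match Table 7.

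**2. Timepoints that depend on dose (Period 2).**

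| Day | Above 180 mg BID | 180 mg BID or below | Only above 180 mg BID |
|---|---|---|---|
| Day 5 | Table 17: AM pre-dose, 0.5, 1.5, 2, 4, 6, 8 h; PM 0.5, 1.5, 2, 4, 6, 15 h (13) | Table 18: AM pre-dose, 1.5, 4 h; PM 0.5, 1.5, 4, 15 h (7) | AM 0.5, 2, 6, 8 h; PM 2, 6 h (6 of 13) |
| Days 2-4 | Table 14: pre-dose, 0.5, 2, 4, 8, 11, 13 h (7) | Table 13: pre-dose, 2, 4 h (3) | 0.5, 8, 11, 13 h (4 of 7) |

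**3. Dose mix and the pooled CV (illustration).** Protocol 8.2.2 gives 10 mg once daily to 180 mg BID, so 180/10 = 18-fold per dose. No dose distribution is given, so two log-uniform spreads are assumed. For limits a and b, mean = (b - a)/ln(b/a) and mean square = (b² - a²)/(2 ln(b/a)).
- 60-180 mg: mean 109.2, dose CV 0.314.
- 10-180 mg: mean 58.8, dose CV 0.784.

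Assume concentrations proportional to dose and a CV at fixed dose of 30% or 50%. Pooled CV = √[(1 + CV_dose²)(1 + CV_fixed²) - 1].
- 60-180 mg: 44% or 61%.
- 10-180 mg: 87% or 101%.

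**4. Shape of the Day 5 mean curve (illustration).** The model is one-compartment oral at steady state, with doses at 0 and 9 h daily. Half-life is 11-14 h and tmax 0.75-3 h (Protocol 2.2.1). Each dose adds D[exp(-kt) - exp(-ka·t)], where k = ln 2/half-life and ka solves tmax = ln(ka/k)/(ka - k).

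Within a person, C(8 h)/C(4 h) = 0.777 to 0.827, a fall of 17-22%. The 4 h mean uses everyone; the 8 h mean uses only those above 180 mg BID. With m people assumed at 240 mg BID out of 13 (also assumed) and the rest at dose d:

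pooled ratio = C(8)/C(4) × 240 / {[240m + d(13 - m)]/13}

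| Rest at | m | 240 / mean dose | Pooled 8 h/4 h ratio |
|---|---|---|---|
| 90 mg | 1 | 2.364 | 1.84-1.95 |
| 90 mg | 3 | 1.926 | 1.50-1.59 |
| 90 mg | 5 | 1.625 | 1.26-1.34 |
| 180 mg | 1 | 1.300 | 1.01-1.08 |
| 180 mg | 3 | 1.238 | 0.96-1.02 |

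With m = 0 there is no 8 h mean and no effect.

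**5. Morning AUC0-tau from Table 18 profiles.** 9 - 4 = 5 h of the 9 h interval have no sample (56%). In the same model, as a fraction of true AUC0-9:
- Samples to 4 h give 0.45-0.47.
- Extending the line through the 1.5 and 4 h samples gives 0.95-1.05.
- Bridging through the sample 0.5 h after the evening dose gives 1.05-1.13.
- Table 12 sampling to 8 h, extended to 9 h in the same way, gives about 0.99.

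The three-sample AUC0-4 recovers 0.90-0.96 of the true AUC0-4.

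**The case against.** The pooling follows a stated convention and has a reason. Period 1 uses a common escalation ladder, whereas Periods 2 and 3 are titrated individually in a trial of about 16 people, so by-dose cells will often hold one or two. No rule is breached, because Protocol 9.7 concerns parameters, and those are shown by dose. Individual listings and plots are planned, and the tables already carry n, so a timepoint filled by few people would be visible there. All of this stands and limits the weight of the point. It does not make a pooled mean interpretable, and the SAP 11.1 default yields where something else is specified.

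The profile distortion needs a participant above 180 mg BID, and the documents report none. A reader might infer that the Period 2 mean curve will be distorted, or that an 18-fold spread applies on Day 5. Neither is supported. The protocol range describes the first 7 participants' requirements, and its lower end was once daily. Remaining participants start Period 2 at 90 mg BID for at least 3-4 doses, which limits early mixing.

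The text of SAP 10.13, on special considerations for Period 2, is not in the reviewed copy. It could govern the Period 2 summaries as well as AUC0-tau.

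A reader might also infer that the morning AUC0-tau should be dropped in favour of AUC0-4. That does not follow. AUC0-tau is a protocol endpoint, and the two-point extension recovers 95-105% of it in the model. SAP 13.8.1 lets a pharmacokineticist adjudicate imputations, but for implausible or outlying data and not for a gap built into the schedule.

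**Conclusion.** The point holds as a minor one: a cheap improvement to descriptive PK output. As written, the Period 2 and Period 3 concentration means and CVs mix doses, chiefly on Period 2 Days 3-5 and at Week 24. The size is not known, because no dose distribution is given; the CVs above rest on assumed spreads and on proportionality, which Protocol 2.2.1 documents only from 5 to 100 mg.

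The composite mean curve is conditional. It can be marked if a few people exceed 180 mg BID while the rest are near 90 mg, it nearly vanishes if the rest are at 180 mg, and it is absent if nobody exceeds 180 mg BID. In that last case every Day 5 profile is a Table 18 profile. The sampling mismatch does not arise in Period 3.

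For Table 18 profiles about half of the morning AUC0-9 is unobserved. The visible text attaches its extrapolation and fit flags only to half-life and AUC0-inf.

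It would be wrong to conclude that dose-specific exposure is lost: parameters by dose, listings and individual plots remain. No primary endpoint is affected.

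**What to change.** **Concentrations (SAP 13.8.2).** For Period 2, unless 10.13 already covers it, present tables and mean plots at least split at the 180 mg BID threshold that sets the sampling schedule, and by dose received where cells allow. Do the same by dose received in Period 3. In very small cells show individual values without SD or CV. State the dose range, and print n at each timepoint on the mean plots.

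**AUC0-tau (SAP 13.8 and Table 7), only if 10.13 is silent.** Keep the morning AUC0-tau on Period 2 Day 5. Where it comes from a Table 18 profile, flag it as extrapolated under a rule stated in advance, and do not bridge it through the sample after the evening dose. AUC0-4, labelled as partial, may be added as a supplement but not as a replacement.

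**Cost.** SAP wording and table shells only, with no extra blood draws. The price is small cells, some too small for summary statistics, and one more flag in the parameter tables.

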13.8.3 Pharmacokinetics (PK) Data Analysis Methods

PK parameter estimates for CLTX-305 (encaleret) in plasma will be calculated by ICON using standard noncompartmental methods of analysis found in WinNonlin Phoenix version 8.1 or higher (Certara, Princeton, NJ, USA).

For calculation of AUC, BQL values on the leading edge of the profile (i.e., before t_{max}) are set equal to zero in the dataset loaded into WinNonlin (WNL) for PK analysis. BQL values after t_{max} are set to missing. BLQ values embedded between two measurable values will be treated as missing. Actual times will be used in the calculation of PK parameters. If actual times are missing, then nominal times will be used.

Descriptive statistics (n, mean, SD, %CV, median, minimum, maximum, geometric mean, and geometric CV) of PK parameters will be presented for each study dose, visit and period.

PK of CLTX-305 (encaleret) will be assessed by measuring the PK parameters included in Table 7.

Parameter	Description	PK Analysis Notes	SAS Programming Notes
C _{max}	Maximum plasma concentration. Observed peak analyte concentration obtained directly from the experimental data without interpolation, expressed in concentration units	single and multiple doses	Cmax from WNL
t _{max}	Time to reach Cmax in plasma. The time to reach maximum concentration is obtained directly from the experimental data without interpolation and expressed in time units.	single doses and multiple doses	Tmax from WNL

Table 7: PK Parameters

Parameter	Description	PK Analysis Notes	SAS Programming Notes
t _{1/2}	Terminal elimination phase half-life expressed in time units. $t_{1/2}$, will be calculated as ln2/Lambda z, where Lz is as defined below.	Single dose If there is no valid terminal phase and terminal elimination rate constant (Lambda z), t _{1/2} cannot be calculated	HL_Lambda_z from WNL Flag to List only if: AUC_%_obs >20% OR Rsq_< 0.8
Lambda z	First-order rate constant associated with the terminal (log-linear) portion of the curve. Estimated by linear regression of time vs. log concentration.	Single dose	Lambda_z from WNL Flag to list only
AUC _{0-t}	Area under the concentration-time curve from time 0 (dosing) to the time of the last quantifiable concentration AUC(0-T) is expressed in concentration*time units.	Single dose Calculated by the linear up/log down method in WNL.	AUClast from WNL
AUC ₀₋₂₄	Area under the concentration-time curve from time 0 (dosing) to 24 hours observed, without interpolation or extrapolation, AUC(0-24) is expressed in concentration*time units.	Single dose Calculated by the linear up/log down method in WNL.	AUC0-24 from WNL

Parameter	Description	PK Analysis Notes	SAS Programming Notes
AUC _{0-inf}	Area under the concentration-time curve from time 0 (dosing) extrapolated to infinity, estimated by summing AUC(0-T) and the extrapolated area, AUC%Extrap, computed by the quotient of the last quantifiable concentration (Clast) and Lz. AUC(INF) = AUC(0-T) + Clast/Lz. AUC(INF) is expressed in concentration*time units.	Single dose Calculated by the linear up/log down method in WNL If there is no valid terminal phase and terminal elimination rate constant (Lambda z), AUC(0- inf) cannot be calculated	AUCINF_obs from WNL Flag to List only if: AUC_%_obs >20% OR Rsq_< 0.8
AUC%Extrap	Percentage of AUC(INF) due to extrapolation from the last quantifiable concentration observed to infinity. AUC%Extrap = [AUC(INF)- AUClast]/ AUC(INF) *100	Single dose	AUC_%Extrap_obs from WNL Flag to List only
Rsq	Goodness of fit statistic for the terminal elimination phase.	Single dose	Rsq_fromWNL Flag to Listonly
AUC _{0-tau}	Area under the concentration-time curve from time 0 to one dosing period tau, tau = 9 hours for the am dose and 15 hours for the pm dose AUC(0-tau) is expressed in concentration*time units.	Multiple dose only Calculated by the linear up/log down method in WNL.	AUC_TAU from WNL
C _{trough}	Trough concentration	Multiple dose only	Cmin from WNL

